7.3.2 Within-Dose Safety Monitoring Rule

For each dose $d = 1, 2, 3$, denote $p(d) = \Pr(\text{DLT at dose } d)$. Assume that each $p(d)$ follows a beta(.35, .65) prior. Applying the method of Thall et al.⁴¹, enrollment to dose d will be stopped if $\Pr[p(d) > .35 | \text{data}] > .85$. This criterion will be applied continuously starting at $n = 3$, which implies that accrual to d should be stopped if [number of DLTs] / [number of patients evaluated] is greater than or equal to 3/3 or 4/5. To apply this safety rule for each dose to 2 cohorts of size 3 each may or may not require suspension of accrual. For each dose (a) once 1 or more pats in cohort 1 (pats #1,2,3) have “No toxicity” by day 42 of followup, cohort 2 may begin enrollment, and (b) once 2 or more pats in cohorts 1 and 2 combined (pats #1,2,3,4,5,6) have “No toxicity” by day 42 of follow up, the last patient 7 may be enrolled. This rule has the following operating characteristics.

Operating characteristics of the within-dose safety monitoring rule

True $p(\text{DLT} d)$	$\Pr(\text{Stop accrual to } d)$	Sample Size	Quartiles
.35	.163	7, 7, 7	
.55	.497	4, 7, 7	
.60	.601	4, 6, 7	
.65	.607	3, 4, 7	

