7.4 Enrichment

If enrollment to a dose d is stopped early at $n(d) = 3$ or 6 before 7 patients are treated, then the remaining $7 - n(d) = 1$ or 4 patients will be randomized between the remaining two doses. If enrollment to 2 doses is stopped early, then all remaining patients, up to $N_{\text{max}} = 21$, will be treated at the one remaining dose. If enrollment to all 3 doses is stopped early, then the trial will be stopped with no dose selected.

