7.6 Trial Conduct

The Biostatistics Department Clinical Trial Conduct Website will be used to assign a dose to each patient at enrollment. This will be set up and overseen by a Research Statistician in the Biostat Dept to be designated by [name] prior to re-starting the trial at patient number 3, using a randomization sequence provided by [name]. The Principal Investigator and designated personnel in the SCT Dept will be responsible for recording all baseline covariates and outcome variables and implementing the within-dose stopping rule in terms of DLTs.

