7.7 Summary Reports

The investigator is responsible for completing a toxicity summary report and submitting it to the IND Office, Medical Affairs and Safety Group, for review and approval. This should be submitted after the first, the first three, and the first five evaluable patients per cohort, have completed 42 days post-first CYT107 injection.

A copy of the cohort summary should be placed in the Investigator's Regulatory Binder, under "Sponsor Correspondence".

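### The within-dose stopping rule is inconsistent: at 4 DLTs in 6 patients the criterion stops the dose while an enrolment condition admits patient 7; the boundary wording, one table row and Section 7.4 also disagree with the criterion

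*Combined protocol and SAP*

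**What the plan says.** Section 7.3.2 of the combined protocol and SAP gives each dose's DLT probability p(d) a beta(.35, .65) prior and stops enrolment to the dose if Pr[p(d) > .35 | data] > .85. On timing it says "This criterion will be applied continuously starting at" n = 3. It then translates the criterion into counts: "accrual to d should be stopped if [number of DLTs] / [number of patients evaluated] is greater than or equal to 3/3 or 4/5".

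Two enrolment conditions follow. Under (a), cohort 2 may open when at least 1 of the first 3 patients has no toxicity by day 42. Under (b), patient 7 may enter "once 2 or more pats in cohorts 1 and 2 combined" have no toxicity by day 42. The section then presents a table, "Operating characteristics of the within-dose safety monitoring rule", with stopping probabilities .163, .497, .601 and .607 at true DLT rates .35, .55, .60 and .65. The sample-size quartiles are 7, 7, 7; 4, 7, 7; 4, 6, 7; and 3, 4, 7.

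Section 7.4 reallocates patients "If enrollment to a dose d is stopped early at $n(d) = 3$ or 6 before 7 patients are treated", giving 4 or 1 patients to move. It adds: "If enrollment to 2 doses is stopped early, then all remaining patients, up to" 21, are treated at the remaining dose. Section 7.6 makes the investigator and department staff responsible for "implementing the within-dose stopping rule in terms of DLTs". Section 7.7 requires toxicity summaries "after the first, the first three, and the first five evaluable patients per cohort" have completed 42 days.

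**The concern.** This is the plan's only quantitative rule for closing a dose, and safety is part of the primary objective. Four elements should express it identically: the posterior criterion, the printed fractions, the enrolment conditions and the reallocation rule. They do not.

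The sharpest conflict is at 4 DLTs in 6 patients, where the criterion closes the dose and condition (b) lets patient 7 in. The rule is to be implemented in terms of DLTs, so staff may well rely on the printed counts and conditions. The scheduled toxicity summaries come after 1, 3 and 5 evaluable patients, so none falls at n = 6, where condition (b) acts. The discontinuation and removal rules in Sections 4.0 and 8.0 apply to individual patients and do not decide whether a dose stays open.

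The table describes the design only if the criterion, not condition (b), governs at n = 6.

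**Working it through.** **Inputs** (Section 7.3.2): prior beta(.35, .65); threshold .35; cutoff .85; checks from n = 3; planned maximum of 7 per dose.

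**Step 1: the boundary.** With x DLTs in n patients the posterior is beta(.35 + x, .65 + n − x). Its tail above .35 is:

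| n | largest x that continues | smallest x that stops |
|---|---|---|
| 3 | 2/3: .834 | 3/3: .985 |
| 4 | 2/4: .694 | 3/4: .932 |
| 5 | 3/5: .8485 | 4/5: .973 |
| 6 | 3/6: .746 | 4/6: .929 |
| 7 | 3/7: .637 | 4/7: .865 |

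The rule is therefore 3 DLTs in 3 or 4 patients and 4 DLTs in 5 to 7. The printed fractions equal this only if they mean the first n at which 3, and then 4, DLTs trigger a stop. Read as proportions of at least 3/3 or 4/5, they miss 3/4 and 4/6.

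**Step 2: the enrolment conditions.** Condition (a) opens cohort 2 at 2/3 DLTs or fewer, which agrees with the criterion. Condition (b) admits patient 7 at 4/6 DLTs or fewer. The criterion stops at 4/6 and needs at least 3 of 6 patients without toxicity to continue.

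**Step 3: reproduce the table.** Let p be the true DLT rate and q = 1 − p. With checks at n = 3 to 6, the first stop is:
- at n = 3 (3/3): p³;
- at n = 4 (2/3, then a DLT): 3p²q × p = 3p³q;
- at n = 5: impossible, since continuing past n = 4 means at most 2/4, hence at most 3/5;
- at n = 6 (2/4, then two DLTs): 6p²q² × p² = 6p⁴q².

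| p | n = 3 | n = 4 | n = 6 | exact total | table |
|---|---|---|---|---|---|
| .35 | .0429 | .0836 | .0380 | .1645 | .163 |
| .55 | .1664 | .2246 | .1112 | .5022 | .497 |
| .60 | .2160 | .2592 | .1244 | .5996 | .601 |
| .65 | .2746 | .2884 | .1312 | .6942 | .607 |

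Three rows agree within .006. The last is short by .694 − .607 = .087. The number of simulated trials is not given. If it was 1,000 (an assumption), the standard error is √(.694 × .306/1000) = .0146, and the gap is about 6 standard errors. The printed values also rise by .104 from p = .55 to .60 but by only .006 from .60 to .65; the exact rises are .097 and .095. The quartiles in the .65 row (3, 4, 7) do match the exact rule.

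**Step 4: other readings of the text.**

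| Reading | Formula | .35 | .55 | .60 | .65 |
|---|---|---|---|---|---|
| Criterion at n = 3–5, condition (b) overrides at 6 | p³ + 3p³q | .126 | .391 | .475 | .563 |
| Fractions as proportions | p³ + 3p⁴q | .072 | .290 | .372 | .462 |
| Conditions (a) and (b) alone | p³ + 3p⁵q | .053 | .234 | .309 | .396 |
| Criterion at n = 3 and 6 only | p³ + 12p⁴q² + 3p⁵q | .129 | .457 | .558 | .659 |

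In the first reading condition (b) never blocks patient 7: a dose still open after n = 5 has at most 3/5, hence at most 4/6. None of these readings gives the table, and none gives .607 at p = .65.

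The chance that patient 7 is released at 4/6 is 6p⁴q² = .038, .111, .124, .131 if the criterion operates at n = 3–5. It is 12p⁴q² = .076, .222, .249, .262 if only the conditions control accrual.

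**Step 5: Section 7.4.** Under the criterion, stops occur at n = 3, 4 or 6. A stop at n = 4 is the likeliest in every row and makes up 51%, 45%, 43% and 42% of all stops (for example .0836/.1645). The table itself prints quartiles of 4. Section 7.4 names neither this case nor the 7 − 4 = 3 patients it frees.

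**The case against.** The strongest reply is that the criterion is explicit and governs throughout. Condition (b) says only that patient 7 may be enrolled, and it follows a remark about whether accrual needs to be suspended. It can be read as a timing rule for pending day-42 outcomes, with the criterion still able to close the dose at 4/6. That reading is reasonable but is not stated: the conditions are introduced as the way to apply the safety rule, and nothing says the criterion overrides them. The direct exposure is one patient per dose.

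The fractions are presented as a consequence of the criterion, and three table rows support the count reading. This stands: the boundary is ambiguous rather than wrong.

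The .607 may be a one-digit slip or a fault in reading the PDF; the documents cannot settle which. The error understates stopping, so by itself it is a correction and not a hazard.

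On Section 7.4, the general expression 7 − n(d) would give 3 at n = 4. The section also counts patients treated, whereas the boundary counts patients evaluated, so a crossing at 3/4 evaluated could come with 5 or 6 already treated. The stop-at-4 probabilities therefore carry over to reallocation only if accrual waits for outcomes. The table's quartiles of 4 still show that the listed stopping points do not match the rule it describes.

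The proportion and conditions-only readings are extremes, and each requires ignoring the stated criterion.

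**Conclusion.** The concern holds. At 4/6 DLTs Section 7.3.2 gives two opposite instructions, and this is the part that must be resolved. The most defensible measure of its effect is the fall in stopping probability if condition (b) prevails at n = 6: from .165 to .126, .502 to .391, .600 to .475 and .694 to .563 at true rates .35, .55, .60 and .65. That fall is conditional on which instruction is followed; if the criterion governs, the first three table rows are right and only .607 is wrong (.694). The ambiguous boundary wording and the missing n = 4 case are lesser defects of the same rule. The calculations assume independent outcomes with a constant DLT rate, each patient evaluated before the next enters, and early stopping counted only before n = 7.

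**What to change.** Reconcile the criterion, the printed boundary, condition (b) and Section 7.4 into a single rule, and state which element governs if they differ. Specifically:

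- Replace the two fractions with a count boundary for every n. Under enrichment one dose can reach 21 − 3 − 3 = 15 patients, so the list must go beyond 7. For the criterion as stated it is 3 DLTs in 3–4 patients, 4 in 5–7, 5 in 8–9, 6 in 10–11, 7 in 12–14 and 8 in 15.
- State the n at which the rule is checked, and whether n counts treated or evaluated patients.
- Make the stopping points and reallocated numbers in Section 7.4 agree with those checks.
- Recompute the table for the rule adopted. If the criterion at n = 3–6 is kept, .607 becomes .694.

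The cost is wording and table edits, with no change in sample size. The choice affects what the table can claim. With checks only at n = 3 and 6, the stated probabilities at .35, .55 and .60 fall by .034, .040 and .043, and the .65 row becomes .659. If condition (b) is kept at n = 6, they fall by .037, .106 and .126, and the .65 row becomes .563.

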4.0 Treatment Plan and Study Design

CYT107 will not be administered before Day 60 but could be started as late as Day 180 post-CBT or haplo-SCT.

The active treatment period will be from the first injection of CYT107 and for 30 days after the last injection. The follow-up period will be for three years after the last injection.

Patients will be treated with CYT107 by intramuscular route (I.M.)* post CBT or haplo-SCT (from 60 to 180 days), with 1 of 3 doses below:

- 5 mcg/kg/dose for 3 doses, one week apart
- 10 mcg/kg/dose for 3 doses, one week apart
- 20 mcg/kg/dose for 3 doses, one week apart

Enrollment of the first 3 participants will be staggered by 14 days. Accrual in between cohorts will be halted for 30 days after the last patient in each cohort has received the last dose of CYT107.

* If the patient's platelet count is below 35,000, the product may be administered by subcutaneous route.

All patients will receive foscarnet for the management of CMV infection as per Stem Cell Transplantation and Cellular Therapy Department's standard of care.

Dose modifications

Treatment will be permanently discontinued for patients developing grade 3 or 4 GVHD, secondary graft failure, disease relapse, PTLD, PML, grade 2-4 skin rash, or grade 3-4 non-hematological toxicity attributable to CYT107.

Patients who develop grade 2 non-hematological toxicity attributable to the CYT107 will have the next dose withheld until the toxicity resolves to grade 1. If the toxicity resolves within 2 weeks the drug will be administered at the same dose, however if the toxicity takes more than 2 weeks to resolve the drug will be administered at the next lower level, or permanently discontinued if the patient was already at the lowest level. If the toxicity takes more than 4 weeks to improve to grade 1, the CYT107 will be permanently discontinued

For patients who at study entry have grade 0, 1 or 2 hematological toxicity and develop grade IV hematological toxicity attributable to the CYT107 will have the next dose withheld until the toxicity resolves to grade 2. If the toxicity resolves within 2 weeks the drug will be administered at the same dose, however if the toxicity takes more than 2 weeks to resolve the drug will be administered at the next lower level, or permanently discontinued if the patient was already at the lowest level. If the toxicity takes more than 4 weeks to improve to grade 2, the CYT107 will be permanently discontinued

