7.0 Statistical Considerations

7.1 Outcomes and Covariates

7.1.1 Primary Outcomes

Toxicity. Dose limiting toxicity (DLT) is defined as any of the following events: grade 3 or 4 GVHD, secondary graft failure, disease relapse, development of PTLD, development of PML, grade 2 organ failure or grade 2-4 skin rash, fatigue, AST and ALT elevations, allergic anaphylaxis, or hemolytic anemia, attributable to CYT107, or death, occurring within 42 days of the first CYT107 injection.

Biological Responses. The absolute number and percentage of total White Blood Cells (WBCs) consisting of T-cells and of B-cells will be observed at 1, 3, 6, 9 and 12 months.

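### The DLT stopping rule in 7.3.2 leaves evaluated patients, pending patients and finality of closure undefined, and its operating characteristics assume that nobody is pending

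*Combined protocol and SAP*

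**What the plan says.** All references are to the combined protocol and SAP.

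- **Rule (7.3.2).** The prior is given as "Assume that each $p(d)$ follows a beta(.35, .65) prior". A dose stops when the posterior probability that its DLT rate exceeds .35 is above .85. The check is continuous from the third patient. In counts, "accrual to d should be stopped if [number of DLTs] / [number of patients evaluated] is greater than or equal to 3/3 or 4/5".
- **Enrolment conditions (7.3.2).** (a) Patients 4 to 6 at a dose may enter once at least one of patients 1 to 3 has passed day 42 without toxicity. (b) Patient 7 may enter once at least two of patients 1 to 6 have done so. The section allows that accrual may need to be suspended, but does not say when.
- **DLT window (7.1.1).** An event counts if it is one "occurring within 42 days of the first CYT107 injection".
- **Halt (4.0).** "Accrual in between cohorts will be halted for 30 days after the last patient in each cohort has received the last dose of CYT107". With three weekly doses this runs to about day 14 + 30 = 44 of the last patient, later than condition (a) requires.
- **Reallocation (7.4).** "If enrollment to a dose d is stopped early at" three or six patients, the remaining places go to the other doses. No route to reopening is given.
- **Reports (7.7).** Toxicity summaries are based on evaluable patients who have completed 42 days.
- **Stated stopping probabilities (7.3.2).** .163, .497, .601 and .607 at true DLT rates of .35, .55, .60 and .65. No accrual rate or distribution of time to DLT accompanies them.

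**The concern.** A DLT can be known on the day it happens, whereas absence of a DLT is known only at day 42. If the count of evaluated patients takes each result as it arrives, the evaluated group at an interim look is weighted towards DLTs. A dose could then close on a fraction that its own enrolled patients later overturn. If instead everyone enters the count at day 42, condition (b) can admit patient 7 before an unfavourable result among patients 4 to 6 is counted, so a toxic dose stops less often than stated. The text does not choose between these readings, and the table reflects neither under the 7.3.2 conditions. With seven places per dose, an early closure under 7.4 takes patients from a small comparison, and a late one treats more patients at a toxic dose.

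**Working it through.** **1. Boundary.** After x DLTs in n patients the posterior is beta(.35 + x, .65 + n − x). The probability that the rate exceeds .35 is:

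| x/n | Probability | Above .85? |
|---|---|---|
| 2/3 | .834 | no |
| 3/3 | .985 | yes |
| 3/4 | .932 | yes |
| 3/5 | .8485 | no |
| 4/5 | .973 | yes |
| 3/6 | .746 | no |
| 4/6 | .929 | yes |

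So 3/4 and 4/6 are stopping results, although the printed list gives only 3/3 and 4/5. The table's sample-size quartiles confirm 3/4: the lower quartile is 4 at rates .55 and .60, and a dose can stop at exactly four patients only through 3/4, since 4/4 would have stopped at 3/3.

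**2. Reproducing the plan's figures.** Take outcomes in enrolment order, each known before the next entry, with looks after patients 3 to 6. With q = 1 − p:

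Pr(stop) = p³ + 3p²q(p + qp²) + 3pq²·p³

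At p = .35: .0429 + .2389 × (.35 + .65 × .1225) + .4436 × .0429 = .0429 + .1026 + .0190 = .1645.

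| True rate | Enrolment order | Stated |
|---|---|---|
| .35 | .1645 | .163 |
| .55 | .502 | .497 |
| .60 | .600 | .601 |
| .65 | .694 | .607 |

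Three rows agree, so the table was evidently computed with nobody pending. The .65 row does not reproduce.

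**3. How a pending patient changes the answer.** Suppose cohort 1 gives two DLTs and one patient clear at day 42. Three more enter, and one has a DLT on day 20 while two are pending. On onset counting the dose is at 3/4 (.932, stop). If both pending patients finish without a DLT, the same six are at 3/6 (.746, no stop).

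**4. Limiting case under the Section 4.0 halt.** If cohort 1 is complete and every cohort-2 DLT is seen before any cohort-2 non-DLT, the middle term becomes 3p²q(1 − q³). At p = .35: .0429 + .2389 × .7254 + .0190 = .235. This is the worst ordering, not an expected value.

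**5. Simulation.** Assumptions not in the documents: exponential gaps between patients at one dose with means of 1 to 4 weeks, DLT times uniform over 42 days, and permanent closure.

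| Enrolment restriction | DLT counted | p = .35 | p = .60 |
|---|---|---|---|
| 7.3.2 conditions | at onset | about .18–.20 | – |
| 7.3.2 conditions | at day 42 | about .12–.13 | about .47–.50 |
| 4.0 halt | at onset | about .19–.22 | – |
| 4.0 halt | at day 42 | about .165 | about .60 |
| Stated | – | .163 | .601 |

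Some runs gave .21 in the first row at a one-week gap. Of the .18 to .20, about .06 to .09 are closures that complete data on the enrolled patients would reverse. With mean gaps near 12 weeks the excess at .35 disappears (.16 to .17). DLT timing also matters: under the 7.3.2 conditions, with mean gaps from 7 to 120 days, onset counting gives .174 to .249 with early DLTs and .157 to .185 with late ones. At a true rate of .20, onset counting with uniform times gives about .04 to .05, against .033 in enrolment order.

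**The case against.** A reader might infer that the rule as written closes acceptable doses more often than .163. The documents do not support that.

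- **Onset counting is a reading, not text.** Section 7.7 works from patients who have completed 42 days, and 7.4 expects closure at three or six patients. Both suggest cohort-end evaluation, under which the stopping probability at .35 is at or below the stated value apart from rounding. This stands, and it is why the point is ambiguity rather than a proven excess. But 7.7 governs reports, not the rule, and day-42 counting under the 7.3.2 conditions misses the .60 row.
- **Accrual is already held in the example.** Only one patient has cleared day 42, so condition (b) keeps patient 7 out. When a pending patient clears, the count is 3/5 (.8485, no stop). The example matters only if closure at 3/4 is final, which the plan leaves open. The loss is then one place (7 − 6).
- **3/4 is not in the printed list.** Taking the list literally gives at most .129 at .35 even in the worst ordering. That cannot be the rule behind the table, whose quartiles need 3/4.
- **A closed dose might seem to lose its candidacy as optimal biological dose.** Section 7.5.3 does not exclude closed doses, and 7.4 rules out selection only when all three stop.
- **The size depends on assumptions.** It does. A rate of .35 is also the rule's own limit, so extra stopping there is on the cautious side, and the rise at .20 is about one percentage point.

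**Conclusion.** The point holds as a gap in specification with a measurable effect. The rule does not say when a DLT enters the count, how pending patients are treated or whether closure is final. The table describes a sequence in which every outcome is known before the next entry. Under the 7.3.2 conditions at gaps of 1 to 4 weeks, onset counting raises the probability at .35 by roughly 2 to 4 percentage points, while day-42 counting lowers it by 3 to 4 points and lowers the .60 figure by 10 to 13. The table is roughly right at .35 and .60 if the Section 4.0 halt and day-42 counting both apply, and the onset excess at .35 disappears with slow accrual. These sizes rest on assumed gaps, uniform DLT times and permanent closure. The omission of 3/4 and 4/6 from the printed boundary and the failure of the .65 row (.607 against .694) do not depend on those assumptions.

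**What to change.** In 7.3.2:

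1. Define *evaluated*, including when a patient with a DLT and a patient without one enter the count.
2. Print the full boundary: 3/3, 3/4, 4/5 and 4/6.
3. State that if the criterion is met while any enrolled patient at that dose is inside the 42-day window, accrual to it is suspended. Closure and the 7.4 reallocation follow only if the criterion is met on all enrolled patients at that dose, or would be met even if every pending patient had no DLT. Otherwise accrual resumes.
4. Reconcile 7.3.2 with the Section 4.0 halt, the closure sizes in 7.4 and the report timing in 7.7, so that one enrolment sequence applies.
5. Recompute every row, including .65, by simulation under that rule with a stated accrual rate and DLT-time assumption.

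The text change is a few sentences plus a simulation. The operating cost is a pause of up to 42 days at the affected dose, during which nobody is enrolled to it. There is also a statistical cost: at a true rate of .60 the stopping probability falls to about .46 to .51 under the 7.3.2 conditions, or about .57 to .58 under the halt, against the stated .601, with roughly 0.1 to 0.2 more patients treated at that dose on average. The new table should show this, so that the sponsor weighs both errors when settling the rule.
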